5.6.3.2 Urinalysis

Urinalysis is assessed, using dipsticks, at the same visits as biochemistry and hematology.

Urinalysis results will be listed only.

5.6.3.3 Pregnancy Test and Urine THC Screen

Serum pregnancy test results and urine THC screen results will be summarized by treatment arm and visit.

5.6.4 Vital Signs, Other Physical Findings and Other Safety Data

5.6.4.1 Vital Signs

At Visit 1, 3 and B3, systolic and diastolic blood pressure are collected in the sitting, supine and standing positions. At all other visits, systolic and diastolic blood pressure are collected in the sitting position only.

Summaries will be presented by treatment arm for each vital sign parameter at each visit. Change from baseline to each post-baseline visit will also be presented.

Body mass index will be calculated, for each visit in which height and weight are recorded, as:

$$\text{Weight (kg)} \div \text{height (m)}^2$$

A separate table will be produced, by treatment arm and visit, presenting the incidence of patients with vital signs indicative of a medical condition at Visit 1 and indicative of an adverse event after Visit 1.

Based on the criteria presented in Section 8, clinically significant changes from baseline in vital signs measurements and other defined flagged values will be identified at each visit. The number of patients with a clinically significant change from baseline will be summarized by parameter, visit and treatment arm. The number of patients with at least one post-baseline flagged vital sign parameter value will be summarized by parameter, flagged criteria and treatment arm for the blinded phase and repeated for the OLE phase.

5.6.4.2 Electrocardiogram

Summaries will be presented by treatment arm for ventricular rate, PR interval, QRS duration, QT interval and QTcB, at each visit. Change from baseline to each post-baseline visit will also be presented.

A separate table will be produced, by treatment arm and visit, presenting the incidence of patients with an ECG indicative of a medical condition at Visit 1 and indicative of an adverse event after Visit 1.

Based on the criteria presented in Section 8, defined flagged values will be identified at each visit. The number of patients with at least one post-baseline flagged ECG parameter value will be summarized by parameter, flagged criteria and treatment arm for the blinded phase and repeated for the OLE phase.

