## 6.1 Inclusion Criteria

For inclusion in the study, patients must fulfil ALL of the following criteria:

- 6.1.1 Patient is male or female aged between one and 65 years inclusive.
- 6.1.2 Patient and/or parent(s)/legal representative is willing and able to give informed consent/assent for participation in the study (see Section 15.2).
- 6.1.3 Patient and their caregiver are willing and able (in the investigator's opinion) to comply with all study requirements (including accurate diary and IVRS completion).
- 6.1.4 Well-documented clinical history of epilepsy, which is not completely controlled by their current AEDs.
- 6.1.5 Clinical diagnosis of TSC according to the criteria agreed by the 2012 International Tuberous Sclerosis Complex Consensus Conference.
- 6.1.6 Taking one or more AEDs at a dose which has been stable for at least four weeks prior to screening.
- 6.1.7 All medications or interventions for epilepsy (including ketogenic diet and any neurostimulation devices for epilepsy) must have been stable for one month prior to screening and the patient is willing to maintain a stable regimen throughout the study.
- 6.1.8 Patient is willing to keep any factors expected to affect seizures stable (such as the level of alcohol consumption and smoking).
- 6.1.9 Patient and/or parent(s)/legal representative is willing to allow the responsible authorities to be notified of participation in the study, if mandated by local law.

6.1.10 Patient and/or parent(s)/legal representative is willing to allow his or her primary care practitioner and consultant (if they have one) to be notified of participation in the study, if mandated by local law.

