## 7.2 Randomization

The allocation of IMP to treatment number will be done according to a randomization schedule produced by an independent statistician. The randomization schedule will be held centrally and not divulged to any other person involved in the study until the database has been locked and unblinding authorized by the relevant GW personnel. For access to blinded treatment assignment, see Section 8.5.

The randomization will be stratified by age group (1–6 years, 7–11 years, 12–17 years and 18–65 years).

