#### 9.2.8 12-Lead Electrocardiogram

A 12-lead ECG will be performed after five minutes in a supine position, if possible. A physician must review the ECG and any abnormal findings considered to indicate significant medical history or AEs must be recorded appropriately in the CRF. Additional ECG measurements can be taken at any time during the study, if clinically indicated.

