5. STATISTICAL METHODS

5.1 General Considerations

In all tables, listings and figures for the double-blind phase, the trial medications will be referred to and labelled as per Table 1.

Table 1 Blinded Phase Trial Treatments

Endpoint	Actual Treatment	Treatment Label
Efficacy	Pooled Placebo	Placebo
Safety	25 mg/kg/day Placebo	Placebo 25 mg/kg
	50 mg/kg/day Placebo	Placebo 50 mg/kg
All	25 mg/kg/day GWP42003-P	25 mg/kg
All	50 mg/kg/day GWP42003-P	50 mg/kg

For safety tables where placebo is split by dosing volume, an additional Pooled Placebo column will be included.

For OLE tables, columns will be included for treatment received during the double-blind phase (GWP42003-P or placebo, i.e. not split by dose) and overall.

In all tables, listings and figures, the trial visits will be referred to and labelled as per Table 2.

Table 2 Trial Visits

Actual Visit	Visit Label
Visit 1: Screening	Day -35
Visit 2: Day -28, baseline visit	Day -28
Visit 3: Day 1, Randomization	Day 1
Visit 4: Day 15	Day 15
Visit 5: Day 29	Day 29
Visit 6: Day 43	Day 43
Visit 7: Day 57	Day 57
Visit 8: Day 71, Telephone	Day 71
Visit 9: Day 85	Day 85
Visit 10: Day 113	End of Treatment
Visit 11: Day 123	End of Taper
Visit 12: Day 151	Safety Follow-Up
Visit B1: Day 1, Enrollment	OLE Day 1
Visit B2: Day 15	OLE Day 15
Visit B3: Day 36	OLE Day 36
Visit B4: Day 92	OLE Day 92
Visit B5: Day 141, Re-stocking of supplies	OLE Day 141
Visit B6: Day 183	OLE Day 183
Visit B7: Day 232, Re-stocking of supplies	OLE Day 232
Visit B8: Day 274	OLE Day 274
Visit B9: Day 323, Re-stocking of supplies	OLE Day 323
Visit B10: Day 365	OLE End of Treatment
Visit B11: Day 375	OLE End of Taper
Visit B12: Day 389	OLE Post-taper Safety Telephone Call
Day 403	OLE Follow-Up

Unless stated otherwise, continuous variables will be summarized showing the number of non-missing values (n), mean, standard deviation, median, minimum and maximum and categorical variables will be summarized showing the number and percentage of patients falling in each category. For continuous summaries of seizure frequency, the lower and upper quartiles will also be presented.

Minimum and maximum values will be presented to the same decimal precision as the raw data. Mean and median will be presented to one more decimal place than the raw data, and standard deviation to 2 more decimal places than the raw data. Percentages will be presented to one decimal place.

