Appendix 3 Defined Flagged Values in ECG Parameters

Defined flagged values that will be used to identify low or high ECG parameters (See Section 5.6.4.2) are presented in Table 11.

Table 11 Defined Flagged Values for ECG Parameters

ECG Parameter	Flag
QTc	> 450, > 480, > 500

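### The SAP names only Bazett-corrected QT and its QTc flags state no formula or unit, so absolute flag counts can partly reflect heart rate; adding Fridericia beside it would show how much.

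*SAP*

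**What the plan says.** SAP 5.6.4.2 (Electrocardiogram) lists what is tabulated: "Summaries will be presented by treatment arm for ventricular rate, PR interval, QRS duration, QT interval and QTcB, at each visit". It adds: "Change from baseline to each post-baseline visit will also be presented". No other QT correction appears in the protocol or the SAP.

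SAP Appendix 3, Table 11, sets the flags for a parameter labelled only QTc: "> 450, > 480, > 500". It gives no correction formula, unit or age-specific limit. The count is per patient: "The number of patients with at least one post-baseline flagged ECG parameter value will be summarized by parameter, flagged criteria and treatment arm". The table is produced for the blinded phase and again for the open-label extension (OLE).

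Eligibility covers a wide age range (Protocol 6.1): "Patient is male or female aged between one and 65 years inclusive". Three of the four randomization strata are under 18 (Protocol 7.2): "1–6 years, 7–11 years, 12–17 years and 18–65 years". On recording conditions, Protocol 9.2.8 says: "A 12-lead ECG will be performed after five minutes in a supine position, if possible".

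For safety tables that split placebo by dosing volume, SAP 5.1 says that "an additional Pooled Placebo column will be included".

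**The concern.** Bazett and Fridericia agree at 60 bpm and diverge on either side of it. If the flags are applied to QTcB, two patients with the same QTcF can fall on opposite sides of a fixed limit because their heart rates differ. A reader of the flag table then cannot tell how much of a count comes from rate and how much from repolarization.

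Three features of the plan add to this:

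- One flagged value at any post-baseline ECG is enough to count the patient. Protocol Appendix 1 schedules seven post-baseline ECGs through end of treatment (four hours after the first dose, then Visits 4, 5, 6, 7, 9 and 10), and an eighth at Visit 11 for patients who taper.
- The ECG flags do not require the limit to have been unmet at baseline. The liver flags in SAP 5.6.3.1 do. A patient whose rate is always fast can therefore be flagged without any change.
- Supine rest is required only where it can be achieved, so a resting rate is not assured.

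What is at stake is how a descriptive cardiac safety table is read, above all in the OLE, where every patient receives GWP42003-P.

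**Working it through.** The plan gives no figure for the flags to reproduce, so the check is on the formulas.

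**Inputs from the documents:** QTcB as the only named correction (SAP 5.6.4.2), limits of 450, 480 and 500 (SAP Table 11; milliseconds assumed, as no unit is given), and ages 1 to 65 (Protocol 6.1).

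**Assumptions, with no source in the documents:** heart rates of 50 to 140 bpm, and a normal QTcF distribution with mean 390 to 410 ms and SD 20 ms.

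**Step 1, ratio.** With RR = 60/HR, QTcB = QT/RR^(1/2) and QTcF = QT/RR^(1/3). Hence QTcB/QTcF = RR^(-1/6) = (HR/60)^(1/6).

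**Step 2, QTcF value at which each Bazett limit is crossed** (limit divided by ratio):

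| HR (bpm) | QTcB/QTcF | >450 | >480 | >500 |
|---|---|---|---|---|
| 50 | 0.970 | 464 | 495 | 515 |
| 60 | 1.000 | 450 | 480 | 500 |
| 80 | 1.049 | 429 | 458 | 477 |
| 100 | 1.089 | 413 | 441 | 459 |
| 120 | 1.122 | 401 | 428 | 445 |
| 140 | 1.152 | 391 | 417 | 434 |

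Below 60 bpm the direction reverses, and a Bazett flag fires later than a Fridericia flag.

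**Step 3, illustrative chance of a flag on one ECG.** For QTcF ~ N(400, 20), P(flag under QTcB) = 1 − Φ((limit/ratio − 400)/20). At 120 bpm and >450 this is 1 − Φ((400.9 − 400)/20) = 48%.

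| HR (bpm) | >450, QTcF | >450, QTcB | >480, QTcB | >500, QTcB |
|---|---|---|---|---|
| 60 | 0.6% | 0.6% | about 0% | about 0% |
| 80 | 0.6% | 7.4% | 0.2% | 0.01% |
| 100 | 0.6% | 25% | 2.1% | 0.15% |
| 120 | 0.6% | 48% | 8.4% | 1.2% |

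Across means of 390 to 410 ms at 120 bpm:

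- >450: 29% to 68% under QTcB, against 0.1% to 2.3% under QTcF.
- >480: 3.0% to 18.9% under QTcB, against 0.02% or less.
- >500: 0.3% to 3.8% under QTcB, against about 0%. At 140 bpm the QTcB range is 1.4% to 11.4%.

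Counting a patient after any one of seven or eight ECGs raises the per-patient figures further.

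**Step 4, sensitivity of the arm contrast.** At a fixed QTcF of 400 ms, moving from 100 to 105 bpm raises QTcB by 3.6 ms, and from 120 to 125 bpm by 3.1 ms. Moving from 100 to 110 bpm raises it by 442.5 − 435.5 = 7.0 ms. With no treatment effect on heart rate, these shifts do not arise systematically between arms.

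**The case against.** The case on the other side is substantial, and most of it stands.

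- **The algebra compares two formulas and does not show that Bazett is wrong.** If QT scaled as RR^(1/2) in these patients, QTcB would be flat and QTcF would under-correct. The documents give no QT–RR relation and nothing that makes Fridericia the reference for young children. A reader might infer that flagged children do not have prolonged repolarization; the documents do not support that.
- **Fast heart rates are assumed.** SAP Table 10 flags pulse above 100, but as a generic limit for all ages. It is not evidence of the rates to be expected on ECG.
- **Table 11 does not say Bazett.** Reading it that way is an inference from QTcB being the only corrected QT named. What is certain is that the formula and unit are unstated.
- **Randomization protects the contrast.** Inflation common to all arms cancels in expectation. A reader might infer that the flags will hide or create a drug signal; that needs a treatment effect on heart rate, which neither document suggests.
- **The components are shown.** Uncorrected QT, ventricular rate and change from baseline appear by arm and visit, and a physician reviews every ECG (Protocol 9.2.8).
- **No rule depends on the flags.** The withdrawal criteria in Protocol 10 contain no QTc value.

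Two points survive. Summaries of QT and ventricular rate by arm do not show which individual flags depend on the choice of correction. The protection from the placebo comparison does not extend to the OLE.

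**Conclusion.** The point holds as a low-cost improvement to safety reporting. It does not show a bias in the trial's conclusions. Table 11 leaves its formula and unit unstated. If it means QTcB, absolute flag counts can partly reflect heart rate. The size depends on assumed rates and an assumed QTcF distribution: it is large for >450, moderate for >480, and small for >500 up to 120 bpm.

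A reader might also infer that the flags should move to QTcF alone. That is not supported either: which correction suits the youngest patients is debatable, and nothing in the documents settles it. Reporting both avoids having to choose.

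**What to change.** 1. In SAP Table 11, state the correction formula and the unit for the QTc limits.
2. Derive QTcF from the QT interval and ventricular rate already recorded: QTcF = QT/(60/HR)^(1/3).
3. Summarise QTcF by arm and visit, with change from baseline, beside QTcB in Table 14.2.1 and OLE Table 14.2.1.
4. Report the Appendix 3 flags under both corrections in Table 14.2.2 and OLE Table 14.2.2, so that flags which depend on the correction can be seen.

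The cost is one derived variable and extra rows in four tables. No new data are needed, and efficacy analyses and patient handling are unchanged.

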5.6.4.3 Physical Examination

Any relevant findings at screening are included as part of the patient's medical history. Any changes seen after screening that are indicative of an AE are to be recorded as such on the AE form and included as part of the AE summaries.

Additionally, height and weight are recorded as part of the physical examination. Height and weight will be summarized and listed together with the vital signs parameters.

Incidence of patients with a physical examination indicative of a medical condition at Visit 1 and indicative of an adverse event after Visit 1 will be summarized by treatment arm and visit.

5.6.4.4 Columbia-Suicide Severity Rating Scale

The C-SSRS is completed for patients who are 6 years and older and capable of understanding and answering the questions, in the investigator's opinion. Questions are asked on suicidal behavior, suicidal ideation and intensity of ideation. At the screening visit, questions are in relation to lifetime experiences and all subsequent questioning in relation to the last assessment.

The following C-SSRS data will be summarized by treatment arm at each visit for patients in the safety analysis set:

- Incidence of the following suicidal ideation:
 - Wish to be dead.
 - Non-specific active suicidal thoughts.
 - Active suicidal ideation with any methods (not plan) without intent to act.
 - Active suicidal ideation with some intent to act, without specific plan.
 - Active suicidal ideation with specific plan and intent.
- Incidence of the following suicidal behavior:
 - Actual attempt.
 - Interrupted attempt.
 - Aborted attempt.
 - Preparatory acts or behavior.
 - Suicidal behavior.
 - Completed suicide.

5.6.4.5 Inpatient Hospitalizations due to Epilepsy

The number of inpatient epilepsy-related hospitalizations since the previous visit are recorded at every visit starting from Visit 2.

The number of patients with inpatient epilepsy-related hospitalizations will be presented by visit, including OLE visits.

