## 9.1.1.2 Visit 2 (Day -28, Baseline)

This visit will occur 7 days after Visit 1. A visit window of  $\pm$ 7 days from the scheduled visit is permitted to ensure ESC confirmation of seizure classification, but it is preferred that the visit is performed on the scheduled visit day where possible.

Attendance of the patient is not required for this visit provided the primary caregiver is able to attend and that this caregiver (not the patient) will be responsible for seizure identification, IVRS use, and paper diary completion. However, it is preferred that the patient attend where possible.

The following observations will be made at Visit 2: review of concomitant medications (including AEDs), AEs and epilepsy-related hospitalizations.

Patients who satisfy all inclusion and none of the exclusion criteria specified in Section 6 will begin the 28 (+3)-day baseline period. The investigator will review and train the patient or their caregiver to identify the patient's expected seizure types. Patients or their caregivers will be issued with IVRS details and will be instructed on how to use it to record daily seizure information. Patients or their caregivers will also be given a paper diary to record usage of IMP, rescue medication, concomitant AEDs and AEs and will be instructed on how to do so.

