#### 9.2.16 Adverse Events

Any adverse changes in the patient's medical condition, following completion of the consent form by the patient, will be recorded on the CRF as AEs, questioning the patient further if necessary. All AEs\* occurring during the study, whether or not attributed to the IMP, observed by the investigator or reported by the patient will be recorded in the CRF.

\*For the patient's expected seizure types, these do not routinely require documentation as AEs. However, any worsening, including change in the pattern or severity of seizures, must be documented as an AE. As part of the ongoing safety review, the SMC will monitor any worsening of seizures, including change in the pattern or severity. Any AE which meets SAE criteria should still be reported as a SAE.

SAEs must be reported to GW Pharmacovigilance Department (PVD) within 24 hours of discovery or notification of the event, and recorded in the CRF.

Refer to Section 12 for definitions, procedures and further information.

The number of inpatient hospitalizations that are, in the investigator's opinion, due to epilepsy will be recorded in the patient's CRF and through the SAE reporting process.

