# 13.6.5.4 Vital Signs, 12-Lead Electrocardiogram, Physical Examination and Other Safety Data

Vital signs, ECG, physical examination, number of inpatient hospitalizations and C-SSRS data will be summarized for the safety analysis set, at screening, baseline and at each time point during the treatment period using appropriate summary statistics. Changes in the vital signs and number of inpatient hospitalizations from baseline to end of treatment will also be summarized. Details of menstruation cycles (in females) will be summarized and listed as appropriate.

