3.3.2 Secondary Efficacy Endpoints

Blinded Phase:

The following endpoints will be compared between treatment arms over the 16-week, double-blind treatment period (all changes relative to baseline):

Key:

1. Number of patients considered treatment responders defined as those with a $\geq 50\%$ reduction in TSC-associated seizure frequency (see Section 5.1.3.7).
2. Change in Caregiver Global Impression of Change (CGIC) or Subject Global Impression of Change (SGIC) score.
3. Change in total seizures.

Other:

Antiepileptic Efficacy Measures:

- Number of patients considered treatment responders defined as those with a $\geq 25\%$, $\geq 50\%$, $\geq 75\%$ or 100% reduction in TSC-associated seizure frequency.
- Number of patients experiencing a $> 25\%$ worsening, $- 25$ to $+ 25\%$ no change, 25–50% improvement, 50–75% improvement or $> 75\%$ improvement in TSC-associated seizure frequency.
- Change in number of TSC-associated seizure-free days.
- Change in number of ‘other’ seizures (absence, myoclonic, focal sensory and infantile/epileptic spasms).

Growth and Development (in patients less than 18 years old):

- Change in serum insulin-like growth factor-1 (IGF-1) levels.
- Change in Tanner Staging score (for patients aged 10–17 [inclusive]).

Quality of Life:

- Changes in the Quality of Life in Childhood Epilepsy (QOLCE; patients 2–18 years) or Quality of Life in Epilepsy (QOLIE-31-P; patients 19+ years) score.
- Change in Physician Global Impression of Change (PGIC) score.

Safety and Tolerability:

- AEs.
- Clinical laboratory parameters.
- 12-lead electrocardiogram (ECG).
- Physical examination parameters.
- Vital signs.
- Columbia-Suicide Severity Rating Scale (C-SSRS: 19+ years) or C-SSRS Children’s (6–18 years) score, where applicable.
- Number of inpatient hospitalizations due to epilepsy.
- Abuse liability.
- Effects on menstruation cycles (in females).

Open Label Extension:

The following endpoints will be assessed relative to the pre-randomization baseline of the blinded phase:

Key:

- Percentage change in number of TSC-associated seizures (average per 28 days).
- Number of patients considered treatment responders defined as those with a $\geq 50\%$ reduction in TSC-associated seizure frequency.
- Change in CGIC or SGIC score.
- Change in total seizures.

Other:

Antiepileptic Efficacy Measures:

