Table 13.3.2	Shift Table for Biochemistry Laboratory Parameters – Based on Toxicity Limits	Safety Analysis Set
Table 13.3.3	Shift Table for eGFR – Based on Derived Grades	Safety Analysis Set
Table 13.4	Summary of Liver Parameter Flags	Safety Analysis Set
Table 13.5	Incidence of Laboratory Abnormalities	Safety Analysis Set
Table 13.6	Summary of Pregnancy Test and Urine THC Screen Results	Safety Analysis Set
Table 14.1.1	Summary of Vital Signs	Safety Analysis Set
Table 14.1.2	Incidence of Clinically Significant Changes from Baseline for Vital Signs	Safety Analysis Set
Table 14.1.3	Incidence of Defined Flagged Vital Signs	Safety Analysis Set
Table 14.1.4	Incidence of Vital Signs Abnormalities	Safety Analysis Set

Table Number	Title	Analysis Set
Table 14.2.1	Summary of ECG Parameters	Safety Analysis Set
Table 14.2.2	Incidence of Defined Flagged ECG Parameter Values	Safety Analysis Set
Table 14.2.3	Incidence of ECG Abnormalities	Safety Analysis Set
Table 14.3	Summary of Columbia-Suicide Severity Rating Scale by Type	Safety Analysis Set
Table 14.4	Incidence of Physical Examination Abnormalities	Safety Analysis Set
Table 14.5	Summary of Tanner Stages	Safety Analysis Set
Table 14.6	Summary of Menstruation Details	Safety Analysis Set
Table 14.7	Summary of Patients with Inpatient Hospitalizations due to Epilepsy	Safety Analysis Set
Table 14.8.1	Summary of Plasma Concentrations	Safety Analysis Set
Table 14.8.2.1	Summary of PK Parameters (Overall and by Age Group)	Safety Analysis Set
Table 14.8.2.2	Summary of PK Parameter Metabolite to Parent Ratio (Overall and by Age Group)	Safety Analysis Set
Table 14.9	Summary of Plasma Concentrations of Concomitant Antiepileptic Drugs	Safety Analysis Set
Table 14.10	Summary of Study Medication Use and Behavior Survey	Safety Analysis Set
Table 14.11.1	Summary of Supplemental Drug Accountability Form	Safety Analysis Set
Table 14.11.2	Summary of Supplemental Adverse Event Form	Safety Analysis Set
Table 14.11.3	Summary of Site Classification Form	Safety Analysis Set

Table 18 List of OLE Phase Tables

Table Number	Title	Analysis Set
OLE Table 1.1.1	Summary of Patient Disposition by Site	OLE Safety Analysis Set
OLE Table 1.1.2	Summary of Patient Disposition During by Country	OLE Safety Analysis Set
OLE Table 1.2	Summary of Overall Patient Disposition	OLE Safety Analysis Set
OLE Table 2	Summary of Important Protocol Deviations	OLE Safety Analysis Set
OLE Table 3.1	Summary of Demographic Data	OLE Safety Analysis Set

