Listing 14.2	Clinically Significant Changes from Baseline for Vital Signs	Safety Analysis Set
Listing 14.3.1	ECG Data – Part 1	Safety Analysis Set
Listing 14.3.2	ECG Data – Part 2	Safety Analysis Set
Listing 14.4.1	Columbia-Suicide Severity Rating Scale (C-SSRS) – Suicidal Ideation and Intensity	Safety Analysis Set
Listing 14.4.2	Columbia-Suicide Severity Rating Scale (C-SSRS) – Suicidal Behavior	Safety Analysis Set
Listing 14.4.3	Columbia-Suicide Severity Rating Scale (C-SSRS) – Actual Attempts	Safety Analysis Set
Listing 14.5	Physical Examination	Safety Analysis Set
Listing 14.6	Tanner Stages	Safety Analysis Set
Listing 14.7	Menstruation Details	Safety Analysis Set
Listing 14.8	Inpatient Hospitalizations due to Epilepsy	Safety Analysis Set
Listing 14.9.1	Plasma Concentrations	Safety Analysis Set
Listing 14.9.2	PK Parameters	Safety Analysis Set

Listing Number	Title	Analysis Set
Listing 14.10	Plasma Concentrations of Concomitant Antiepileptic Drugs	Safety Analysis Set
Listing 14.11.1	Study Medication Use and Behavior Survey – Part 1	Safety Analysis Set
Listing 14.11.2	Study Medication Use and Behavior Survey – Part 2	Safety Analysis Set
Listing 14.12.1	Supplemental Drug Accountability Form	Safety Analysis Set
Listing 14.12.2	Supplemental Adverse Events Form	Safety Analysis Set
Listing 14.12.3	Site Classification Form	Safety Analysis Set
Listing 15	Investigators' General Comments	Safety Analysis Set

Table 20 List of OLE Phase Listings

Listing Number	Title	Analysis Set
OLE Listing 1.1.1	Patient Disposition – End of Treatment	OLE Safety Analysis Set
OLE Listing 1.1.2	Patient Disposition – End of Taper	OLE Safety Analysis Set
OLE Listing 1.2	Visit Dates	OLE Safety Analysis Set
OLE Listing 2.1	Important Protocol Deviations	OLE Safety Analysis Set
OLE Listing 6.1	Prior and Concomitant Antiepileptic Therapies	OLE Safety Analysis Set
OLE Listing 6.2	Prior and Concomitant Antiepileptic Drugs	OLE Safety Analysis Set
OLE Listing 6.3	Prior and Concomitant Rescue Medications	OLE Safety Analysis Set
OLE Listing 6.4	Other Prior and Concomitant Medications	OLE Safety Analysis Set
OLE Listing 8.1.1	IVRS Diary Data – Part 1	OLE Safety Analysis Set
OLE Listing 8.1.2	IVRS Diary Data – Part 2	OLE Safety Analysis Set
OLE Listing 8.2.1	Derived TSC-associated, Other and Total Seizure Data	OLE Safety Analysis Set
OLE Listing 8.2.2	Derived Type 1, 3 and 3 Focal Seizure Data and Composite Focal Seizure Score	OLE Safety Analysis Set

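### The protocol requires the number of epilepsy hospitalizations and its change from baseline, but the SAP tabulates only patients hospitalized, visit by visit

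*SAP*

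**What the plan says.** The SAP lists the endpoint among the blinded-phase secondary safety endpoints (3.3.2) as a count: "Number of inpatient hospitalizations due to epilepsy". Protocol 4.1.2 names it in the same terms.

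The count is collected. Protocol 9.2.16: "The number of inpatient hospitalizations that are, in the investigator's opinion, due to epilepsy will be recorded in the patient's CRF". SAP 5.6.4.5: "The number of inpatient epilepsy-related hospitalizations since the previous visit are recorded at every visit starting from Visit 2".

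Protocol 13.6.5.4 asks for two things. Inpatient hospitalizations are to be summarized at screening, at baseline and at each time point in the treatment period. It then adds: "Changes in the vital signs and number of inpatient hospitalizations from baseline to end of treatment will also be summarized".

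The only summary in SAP 5.6.4.5 is: "The number of patients with inpatient epilepsy-related hospitalizations will be presented by visit, including OLE visits". In SAP Appendix 6, Table 14.7 and OLE Table 14.7 share the title "Summary of Patients with Inpatient Hospitalizations due to Epilepsy". Listing 14.8 in each phase is titled "Inpatient Hospitalizations due to Epilepsy". SAP 5.8, which records changes to the planned analysis, lists two other changes and not this one.

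**The concern.** The protocol promises a number of events and a change in that number. The SAP replaces both with a yes/no status per patient per visit, and no document says this was intended.

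Three consequences follow. A patient admitted twice between two visits counts once. A patient admitted in two intervals appears at two visits, so the column cannot be added up to patients. And because each entry covers the time since the previous visit, the entries rest on different lengths of observation, so a reader following the table across visits will see movements that reflect only the schedule. At stake is whether the study report can show a named secondary safety endpoint in the form the protocol set. The primary result is not touched.

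**Working it through.** **1. Required against planned.**

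| Item | Protocol 13.6.5.4 | SAP 5.6.4.5, Tables 14.7 and OLE 14.7 |
|---|---|---|
| Unit | Hospitalizations | Patients with any hospitalization |
| By time point | Yes | Yes |
| Change from baseline to end of treatment | Yes | No |
| Total or unique patients over the treatment period | Not specified | No |

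**2. Length of each interval.** These are differences between scheduled visit days in Protocol 9.1, with Visit 3 as day 0.

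- Visit 1 to 2: 7 days, before the baseline period ("This visit will occur 7 days after Visit 1", window ±7 days).
- Visit 2 to 3: 28 days. Under SAP 5.1.3.1, Visit 3 is the baseline record for clinic-visit endpoints.
- Visit 3 to 9: six steps of 14 days.
- Visit 9 to 10: 112 − 84 = 28 days.
- Visit 10 to 11: 10 days. Visit 11 to 12: 28 days.
- OLE: 14, 21, 56, 49, 42, 49, 42, 49, 42, 10, 14 and 14 days. The longest is B3 to B4: 91 − 35 = 56 days, which matches the eight weeks of supply dispensed at Visit B3.

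The treatment period (112 days) is 112 ÷ 28 = 4 times the baseline period, so unscaled totals would not be comparable either.

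**3. Effect of interval length.** The documents give no hospitalization rate, so I assume a constant rate r per 28 days and show a range. With independent events, the share of patients with at least one hospitalization in t days is 1 − exp(−r × t/28).

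| r per 28 days | 14 days | 28 days | 56 days | 28 vs 14 | 56 vs 14 |
|---|---|---|---|---|---|
| 0.02 | 1.0% | 2.0% | 3.9% | 2.0 | 3.9 |
| 0.05 | 2.5% | 4.9% | 9.5% | 2.0 | 3.9 |
| 0.10 | 4.9% | 9.5% | 18.1% | 2.0 | 3.7 |
| 0.20 | 9.5% | 18.1% | 33.0% | 1.9 | 3.5 |

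Ratios use unrounded shares. At r = 0.05 the table would show 4.9% at Visit 3, 2.5% at each of Visits 4 to 9 and 4.9% at Visit 10: an apparent halving when treatment starts and a doubling at its end, with no change in rate.

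**4. Adding the by-visit counts over Visits 4 to 10.** Per 100 patients, the sum is 6 × (14-day share) + (28-day share). True events are 100 × 4r. Unique patients are 100 × [1 − exp(−4r)].

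| r | Sum of by-visit counts | True events | Unique patients | Sum ÷ unique |
|---|---|---|---|---|
| 0.02 | 8.0 | 8 | 7.7 | 1.03 |
| 0.05 | 19.7 | 20 | 18.1 | 1.09 |
| 0.10 | 38.8 | 40 | 33.0 | 1.18 |
| 0.20 | 75.2 | 80 | 55.1 | 1.37 |

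Under this model the sum comes close to the number of events but overstates unique patients. If admissions cluster in some patients, as repeat admissions may, the sum could fall further below events and further above unique patients. The documents give no basis for sizing that.

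**5. A method already in the SAP.** Rescue medication days are also recorded since the previous visit. SAP 5.5.4.3 sums them over the baseline period (Visit 2 to 3) and the treatment period (Visit 3 to 10), divides by the days in the period, multiplies by 28, and summarizes the change.

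**The case against.** **The by-visit layout is what the protocol asks for.** This stands. Protocol 13.6.5.4 calls for a summary at each time point, so the by-visit table should stay. The gap is what it counts and what is missing beside it.

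**A reader might infer a distortion spanning 7 to 56 days.** The documents do not support that for the randomized comparison. The 7-day interval precedes baseline, the 56-day interval is in the OLE, and the two phases have separate tables. Scheduled intervals during randomized treatment are 14 or 28 days, and the arms share one schedule, so interval length hardly affects the comparison between arms at a given scheduled visit. One reservation: Visit 10 is also the withdrawal visit, so observed time there can differ by arm if withdrawal does.

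**A reader might infer that the trial could not report the endpoint at all.** That goes too far. Counts are collected, Listing 14.8 shows them by patient, and hospitalizations also pass through serious adverse event reporting, which is tabulated by patient and by event (Tables 12.1 and 12.12). Those tables are not limited to epilepsy admissions and give no change from baseline, so they preserve information without supplying the required summary.

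**Visit 3 and Visit 10 both cover 28 days.** They allow an informal comparison of patients affected. It is not a change in number, and it leaves out Days 1 to 85.

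**The endpoint is descriptive and outside the testing hierarchy.** True, and this limits the weight of the point. The protocol also prescribes no particular rate, only appropriate summary statistics.

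**Conclusion.** The mismatch holds. Followed as written, the SAP tabulates neither the endpoint as named nor the change the protocol promises, and the departure is unrecorded. The by-visit counts cannot be added to unique patients and are not comparable across visits. The artefact is about twofold within the blinded phase (ratio 1.9 to 2.0) and about 3.5- to 4-fold between a 14-day interval and the 56-day OLE interval. These sizes rest on a constant rate, independent events, assumed rates of 0.02 to 0.20 per 28 days, and scheduled visit dates. Safety telephone calls also ask about these hospitalizations; I have taken the by-visit table to show clinic and telephone visits only. The missing summary itself rests on no assumption. It is a reporting gap in a secondary safety endpoint. It is not a bias in the comparison of arms at a scheduled visit, and no data are lost.

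**What to change.** Keep the by-visit summary. Add to SAP 5.6.4.5, Table 14.7 and OLE Table 14.7, by arm (for the OLE, in the columns SAP 5.1 sets):

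- the total number of epilepsy hospitalizations;
- the number of patients with at least one;
- the number per 28 days.

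Give each for the baseline period (Visit 2 to 3), the treatment period (Visit 3 to 10 or withdrawal) and the OLE, with the change from baseline to treatment in the number per 28 days. Use the SAP 5.5.4.3 calculation, whose denominator runs to the last recorded value in the period and so allows for early withdrawal. Retitle the tables to match. If the sponsor prefers patient counts only, SAP 5.8 should record and justify that departure from the protocol.

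The cost is one derived variable and a few extra table rows, from data already collected.
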